2.4.4.5 Additional subgroup analyses

- Smoking status at screening (current smokers, former smokers)

For the annualized rate of COPD exacerbation endpoints, treatment by subgroup interaction and its p-value will be derived from a negative binomial model respectively, same as the approach in subgroup analysis specified in [Section 2.4.4.1](#). Summary statistics of exacerbations will be provided within each subgroup. Forest plot of relative risks and corresponding CIs and forest plot of risk differences and corresponding CIs comparing dupilumab dose group vs. placebo for the subgroups will be provided.

For other efficacy endpoints specified in [Section 2.4.4.3](#) and [Section 2.4.4.4.1](#), treatment by subgroup interaction and its p-value will be derived from MMRM models (for continuous endpoints), logistic regression models (for proportion type endpoints) or Cox regression models (for time to event endpoints) respectively. The model will include all the covariates in the main statistical model for the corresponding endpoints plus the subgroup variable (if not one of the covariates adjusted in the main model already) and the subgroup-by-treatment interaction. A p-value for the test of interaction will be provided.

In each subgroup, the endpoints will be analyzed using the same primary analysis approach for their corresponding endpoints in the total population.

- For continuous endpoints, descriptive statistics including number of patients, mean, standard error, and least squares (LS) means for each subgroup will be provided. In addition, difference in LS means and the corresponding 95% confidence intervals (CI) will be provided for each subgroup.
- For proportion type endpoints, odds ratio of being a responder comparing dupilumab to placebo will be provided for each subgroup along with the corresponding 95% CI and

p-value. Descriptive statistics including number and percentage of responders will also be provided for each subgroup.

- For time to event endpoints, hazard ratio and corresponding 95% CI and p values will be estimated for dupilumab versus placebo for each subgroup. The Kaplan-Meier method will be used to derive the probabilities that a patient would experience an event up to specific timepoints for each treatment group within the subgroup. Kaplan-Meier curves will be generated; point probabilities will be calculated. Interval estimates will be calculated using 95% point wise confidence intervals.

In addition, for each subgroup analysis, the forest plot will be provided.

2.4.4.5 Analyses of exploratory efficacy endpoints

2.4.4.5.1 Analyses of other continuous endpoints

For post-bronchodilator FEV1, the rate of change in FEV1 (termed as FEV1 slope) will be compared between dupilumab against placebo. Repeated post-bronchodilator FEV1 after Week 4 and after Week 8 up to Week 52 will be analyzed correspondingly using linear mixed-effects model with treatment, age, sex, height, region (pooled country), ICS dose at baseline (high dose ICS [yes/no]), smoking status at screening (current smokers or not), time since randomization, and treatment-by-time interaction and baseline post-bronchodilator FEV1 as covariates. Intercept and time since randomization are random effects. Individual post-BD FEV1 slope will be calculated as the slope of a linear regression model with the post-BD FEV1 (L) at each visit as the response variable and the time since randomization as the independent variable. Descriptive statistics including number of patients, mean, standard error of the individual post BD FEV1 slopes will be provided. Estimated from the linear mixed-effects model, least squares (LS) means, difference in LS means and the corresponding 95% confidence intervals (CI) will also be provided.

Change from baseline in FVC (percent predicted and absolute change in ml), weekly E-RS symptom scores at all time-points will be analyzed in a similar way as change from baseline in pre-bronchodilator FEV1 at Week 52. Age, sex and height will be included as covariates only in the models for spirometry parameters. Descriptive statistics including number of patients, mean, standard error, and least squares (LS) means will be provided. In addition, difference in LS means and the corresponding 95% confidence intervals (CI) will be provided.

2.4.4.5.2 Analyses of time to first severe COPD exacerbation compared to placebo during the 52-week treatment period

The time to first severe COPD exacerbation will be analyzed using the same approach as that for the analyses of time to first moderate or severe COPD

exacerbation compared to placebo during the 52-week treatment period. Hazard ratio and corresponding 95% CI and p values will be estimated for dupilumab versus placebo. The Kaplan-Meier method will be used to derive the probabilities that a patient would experience an event up to specific timepoints for each treatment group. Kaplan-Meier curves will be generated; point probabilities will be calculated. Interval estimates will be calculated using 95% point wise confidence intervals.

2.4.4.5.3 Analyses of COPD exacerbation utilizing the Exacerbations of Chronic Pulmonary Disease Tool (EXACT)

COPD exacerbation will be derived using EXACT method as specified in the *The Exacerbations of Chronic Pulmonary Disease Tool (EXACT) Patient-Reported Outcome (PRO) User Manual- Scoring guide* (Version 8.0), March 2016.

The annualized event rate of COPD exacerbations assessed by the EXACT over 52 week (a tertiary/exploratory endpoint) will be analyzed in the same way as the primary analysis for the annualized rate of moderate or severe COPD exacerbation events but based on exacerbation defined by EXACT method instead of the adjudicated data of AECOPD page in eCRF. The estimated event rate for each treatment group and its two-sided 95% confidence intervals will be provided. The event rate ratio of dupilumab against placebo, two-sided 95% confidence intervals of the rate ratio will also be provided.

2.4.4.5.4 Analyses of controller medication change after exacerbation

Increase in number of controller medication and/or total daily dose after adjudicated exacerbation during the treatment period will respectively be summarized by treatment group in terms of number of exacerbation events. For patients who discontinue treatment, data collected during the off-treatment period will also be used. Descriptive statistics including number, mean, median, standard deviation, min, and max will be provided, and no statistical testing will be conducted.

2.4.4.6 Missing data handling

For all continuous efficacy endpoints, the details of missing data handling are described in [Section 2.4.4.1](#).

For responder type endpoints, the details of missing data handling are described in [Section 2.4.4.4.2](#).

In addition, the reason and pattern of missing data will be carefully examined and pattern mixture modeling approach and other sensitivity analyses will also be performed as specified in [Section 2.4.4.1](#).

2.4.5 Analyses of safety data

The summary of safety results will be presented by treatment group.

General common rules

All safety analyses will be performed on the safety population as defined in [Section 2.3.2](#), unless otherwise specified, using the following common rules:

- The baseline value is defined as the last available value before the first dose of IMP.
- The potentially clinically significant abnormality (PCSA) values are defined as abnormal values considered medically important by the Sponsor according to predefined criteria/thresholds based on literature review and defined by the Sponsor for clinical laboratory tests and vital signs and ECG [Appendix A]
- PCSA criteria will determine which patients had at least 1 PCSA during the treatment-emergent adverse event period, taking into account all evaluations performed during the treatment-emergent adverse event period, including nonscheduled or repeated evaluations. The number of all such patients will be the numerator for the on-treatment PCSA percentage
- The treatment-emergent PCSA denominator by group for a given parameter will be based on the number of patients assessed for that given parameter in the treatment-emergent adverse event period by treatment group on the safety population.
- For quantitative safety parameters based on central laboratory/reading measurements, descriptive statistics will be used to summarize results and change from baseline values by visit and treatment group. Summaries will include the endpoint value and/or the worst on-treatment value. The endpoint value is commonly defined as the value collected at the end of treatment. If this value is missing, this endpoint value will be the closest value prior to the end of treatment epoch. The worst value is defined as the nadir and /or the peak post-baseline (up to the end of treatment epoch or EOT) according to the direction (minimum or maximum) of the abnormality as defined in the PCSA list
- The analysis of the safety variables will be essentially descriptive and no systematic testing is planned. Relative risks versus placebo and their 95% confidence intervals may be provided, if relevant
- All safety values including unscheduled measurements will be assigned to the appropriate safety analysis visit window defined in [Section 2.5.3](#).

2.4.5.1 Analyses of adverse events

Generalities

The primary focus of adverse event reporting will be on treatment-emergent adverse events. Pretreatment and posttreatment adverse events will be described separately.

If an adverse event date/time of onset (occurrence, worsening, or becoming serious) is incomplete, an imputation algorithm will be used to classify the adverse event as pretreatment, treatment-

emergent, or posttreatment. The algorithm for imputing date/time of onset will be conservative and will classify an adverse event as treatment emergent unless there is definitive information to determine it is pretreatment or posttreatment. Details on classification of adverse events with missing or partial onset dates are provided in [Section 2.5.2](#).

Adverse event incidence tables will present by SOC, HLGT, HLT, and PT, sorted in alphabetical order for each treatment group, the number (n) and percentage (%) of patients experiencing an adverse event. Multiple occurrences of the same event in the same patient will be counted only once in the tables within a treatment phase. The denominator for computation of percentages is the safety population within each treatment group.

Sorting within tables ensures the same presentation for the set of all adverse events within the observation period (pretreatment, treatment-emergent, and posttreatment). For that purpose, the table of all treatment-emergent adverse events presented by SOC and PT sorted by the internationally agreed SOC order and decreasing frequency of PTs within SOCs will define the presentation order for all other tables unless otherwise specified. Sorting will be based on results for the dupilumab 300 mg q2w group.

Analysis of all treatment-emergent adverse events

The following treatment-emergent adverse event summaries will be generated for the safety population.

- Overview of treatment-emergent adverse events, summarizing number (%) of patients with any
 - Treatment-emergent adverse event
 - Serious treatment-emergent adverse event
 - Treatment-emergent adverse event leading to death
 - Treatment-emergent adverse event leading to permanent treatment discontinuation
- All treatment-emergent adverse event by primary SOC, HLGT, HLT, and PT, showing number (%) of patients with at least 1 treatment-emergent adverse event sorted by the SOC internationally agreed order. The other levels (HLGT, HLT, PT) will be presented in alphabetical order
- Number (%) of patients experiencing TEAE(s) presented by PT, sorted by decreasing incidence of PT
- All treatment-emergent adverse events by primary SOC and PT, showing the number (%) of patients with at least 1 treatment-emergent adverse event, sorted by the internationally agreed SOC order and by decreasing incidence of PTs within each SOC in the 300 q2w treatment group
- All treatment-emergent adverse events regardless of relationship and related by primary SOC, HLGT, HLT and PT, showing the number (%) of patients with at least 1 treatment-emergent adverse event, sorted by the internationally agreed SOC order. The other levels (HLGT, HLT, PT) will be presented in alphabetical order

- All treatment-emergent adverse events by maximal severity, presented by primary SOC and PT, showing the number (%) of patients with at least 1 treatment-emergent adverse event by severity (ie, mild, moderate, or severe), sorted by the internationally agreed SOC order and by decreasing incidence of PTs within each SOC in the 300 q2w treatment group
- Number (%) of patients experiencing treatment-emergent adverse event(s) presented by primary and secondary SOC, HLG, HLT, and PT sorted by the internationally agreed SOC order. The other levels (HLG, HLT, PT) will be presented in alphabetical order

A listing of all treatment-emergent adverse events will be presented

Analysis of all treatment emergent serious adverse event(s)

- All treatment-emergent serious adverse events by primary SOC, HLG, HLT, and PT, showing the number (%) of patients with at least 1 serious treatment-emergent adverse event, sorted by the internationally agreed SOC order. The other levels (HLG, HLT, PT) will be presented in alphabetical order
- All treatment-emergent serious adverse events regardless of relationship and related to IMP, by primary SOC, HLG, HLT, and PT, showing the number (%) of patients with at least 1 treatment-emergent serious adverse event, sorted by the internationally agreed SOC order. The other levels (HLG, HLT, PT) will be presented in alphabetical order
- All treatment-emergent serious adverse events by primary SOC and PT, showing the number (%) of patients with at least 1 treatment-emergent serious adverse event, sorted by the internationally agreed SOC order and by decreasing incidence of PTs within each SOC in the 300 q2w treatment group.

A listing of all treatment-emergent serious adverse events will be presented

Analysis of all treatment-emergent adverse event(s) leading to treatment discontinuation

- All treatment-emergent adverse events leading to treatment discontinuation, by primary SOC, HLG, HLT, and PT, showing the number (%) of patients sorted by the internationally agreed SOC order. The other levels (HLG, HLT, PT) will be presented in alphabetical order
- All treatment-emergent adverse events leading to permanent treatment discontinuation or drug interruption, by primary SOC and PT, showing number (%) of patients with at least one TEAE, will be presented by SOC internationally agreed order and by decreasing incidence of PTs within each SOC in the 300 q2w treatment group.

Analysis of Major Cardiovascular Adverse Events (MACE)

- The number and percentage (%) of patients with any treatment-emergent event selected for adjudication will be summarized by primary SOC and PT.
- All events submitted for adjudication will be listed, including the final adjudicated result.
- The number and percentage (%) of patients experiencing a treatment-emergent adjudicated event will be summarized within each treatment group.

- The risk difference (asymptotic 95% CI with continuity correction) will be computed for the dupilumab dose versus placebo. Kaplan-Meier plots to depict the course of onset over time will also be provided.

Analysis of adverse events of special interests (AESI) and other selected AE groupings

- All treatment-emergent adverse events, by selected standardized MedDRA query (SMQ) and PT or by laboratory values (as in ALT elevation), showing the number (%) of patients with at least 1 PT, sorted by decreasing incidence of PTs within each SMQ in the 300 q2w treatment group.
- For each AESI and other selected AE groupings,
 - Number (%) of patients with any specific TEAE
 - Number (%) of patients with any specific serious AE (regardless of treatment emergent status)
 - Number (%) of patients with any specific treatment emergent serious AE
 - Number (%) of patients with any specific AE leading to death
 - Number (%) of patients with any specific TEAE leading to permanent study drug discontinuation
 - Number (%) of patients with any specific TEAE related to IMP reported by investigator
 - Number (%) of patients with any specific TEAE by maximum intensity, corrective treatment, and final outcome
 - Number of any specific TEAE adjusted by the exposure duration
 - Number of patients with any specific TEAE adjusted by the exposure duration at risk. For each specific TEAE, Kaplan-Meier estimates of cumulative incidence at Week 12, 24, 36 and 52 and K-M plot may be provided to depict the course of onset over time if the number of events is large enough.
 - Number (%) of patients with injection site reactions by the related injection.
 - Number (%) of patients with different number of injection site reactions.
- In addition, AESIs reported by the investigator in CRF will be summarized separately.

Analysis of pretreatment adverse events

- All pretreatment adverse events by primary SOC and PT, showing the number (%) of patients with at least 1 pretreatment adverse event, sorted by the internationally agreed SOC order and decreasing incidence of PTs within each SOC in the 300 q2w treatment group.
- All serious pretreatment adverse events by primary SOC and PT, showing the number (%) of patients with at least 1 pretreatment adverse event, sorted by the internationally agreed SOC order and decreasing incidence of PTs within each SOC

- All pretreatment adverse events leading to permanent treatment discontinuation by primary SOC and PT, showing the number (%) of patients, sorted by the internationally agreed SOC order and decreasing incidence of PTs within each SOC
- All pretreatment adverse events leading to death by primary SOC and PT, showing the number (%) of patients, sorted by the internationally agreed SOC order and decreasing incidence of PTs within each SOC
- If only a few patients have pretreatment adverse events leading to permanent treatment discontinuation, a listing will be presented instead of the summary table above.

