1.3 DETERMINATION OF SAMPLE SIZE

The sample size of the study is determined based on power calculations for the primary endpoint of annualized rate of acute moderate or severe COPD exacerbations over the 52-week treatment period. Assuming the number of exacerbations follows a negative binomial distribution with a dispersion parameter of 1, a placebo annualized rate of exacerbations of 1.5, an average treatment duration of 0.95 year (to account for an average of 5% of the planned treatment period with missing data), and a randomization ratio of 1:1 to the two treatment arms, with 924 randomized patients (462 for each treatment arm), the study will have 90% power to detect a 25% relative risk reduction (ie, annualized rate of 1.125 for the dupilumab group) in the annualized rate of moderate or severe COPD exacerbations at the 2-tailed significance level of $\alpha=0.049$ (an administrative penalty of 0.001 will be taken from the significance level used at final analysis due to a planned interim analysis; details are provided in [Section 3](#)).

Patients will be randomized using a 1:1 randomization ratio to dupilumab 300 mg q2w or placebo. Randomization will be stratified by country and by ICS dose (high dose ICS [yes/no]) at baseline.

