2.1.4.1 Adverse events variables

Adverse event observation period

- Pretreatment adverse events are adverse events that developed or worsened or became serious during the screening epoch
- Treatment-emergent adverse events are adverse events that developed or worsened or became serious during the treatment-emergent adverse event period
- Posttreatment adverse events are adverse events that developed or worsened or became serious during the posttreatment epoch

All adverse events (including serious adverse events and adverse events with pre-specified monitoring/of special interests) will be coded to a lower-level term (LLT), preferred term (PT), high-level term (HLT), high-level group term (HLGT), and associated primary system organ class (SOC) using the version of Medical Dictionary for Regulatory Activities (MedDRA) currently in effect at Sanofi at the time of database lock.

The occurrence of adverse events (including serious adverse events and adverse events with prespecified monitoring) will be recorded from the time of signed informed consent until the end of the study.

Cardiovascular assessment

All events submitted for cardiovascular adjudication will be listed and summarized, including the final classification results. A swimmer plot including all events classified as cardiovascular, including cardiovascular death, will also be provided.

Furthermore, events classified as cardiovascular will be evaluated according to the following composite endpoints:

- **Major Cardiovascular Adverse Events (MACE):** cardiovascular death, non-fatal myocardial infarction, or non-fatal stroke
- MACE + hospitalization for unstable angina
- Cardiovascular death: death resulting from myocardial infarction, stroke, pulmonary embolism, heart failure, procedure-related death or other cardiovascular cause.
- Hospitalization: for unstable angina, for atrial fibrillation/flutter, for other symptomatic arrhythmias, for transient ischemic attack.
- Other cardio/cerebrovascular events: non-fatal heart failure, peripheral arterial event, pulmonary embolism, non acute coronary syndrome/myocardial ischemia, others.

Adverse events of special interest (AESI) and other selected AE groupings will be searched based on the criteria in [Table 2](#).

Table 2 - Criteria for adverse events of special interest and other selected AE groupings

AE Grouping	Criteria
AESI	

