3 INTERIM ANALYSIS

A nonbinding futility IA in the study is planned to be performed when approximately 408 patients would have completed Week 12 visit. Guideline for the futility decision will be provided in the DMC charter. The purpose of the IA is to obtain an understanding of the possible drug effect in this population. The IA will be performed by independent statisticians that support the DMC and are separated from personnel involved in the trial conduct. DMC will review the unblinded IA results and recommend action based on the non-binding futility criterion that is specified in the DMC charter and DMC SAP. The DMC will inform a group of senior sponsor individuals whether the criterion is met. If the criterion is met, and only if the criterion is met, the unblinded futility analysis results as well as select additional analyses will be provided to the senior sponsor group. The senior sponsor group will make a decision regarding stopping or continuing the study. The senior sponsor group are the only sponsor individuals that are planned to view this data. A detailed plan will be defined in the DMC charter and DMC SAP, including a plan to describe the processes intended to control access to comparative interim results to preserve trial integrity. People involved in the conduct of the study (patients, Investigators, Study Team, and Project Team) will not have access to the IA results.

At the IA, the efficacy endpoints will be analyzed using the same methods described in the efficacy analyses section ([Section 2.4.4](#)). The analysis population for the IA will be the first 408 patients randomized. The analysis of the endpoints will use all the data collected for the analysis population up to the IA cutoff time. An administrative penalty of 0.001 will be taken from the significance level used at final analysis (ie, two-sided 0.049 will be used for the final analysis).

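### The planned interval for the MACE risk difference is far too narrow if neither arm has an event and somewhat too narrow at one or two events; naming a score interval is a minor change

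*SAP*

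**What the plan says.** SAP Section 2.4.5.1, in the list headed Analysis of Major Cardiovascular Adverse Events, states: "The risk difference (asymptotic 95% CI with continuity correction) will be computed for the dupilumab dose versus placebo". The MACE row of protocol Table 10 (Section 9.4.2) plans the same. SAP Section 2.1.4.1 defines MACE as "cardiovascular death, non-fatal myocardial infarction, or non-fatal stroke".

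For adverse event tables the SAP states: "The denominator for computation of percentages is the safety population within each treatment group". The planned size comes from SAP Section 1.3: "with 924 randomized patients (462 for each treatment arm), the study will have 90% power".

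Neither document names the formula behind the interval, gives a score or exact alternative, or says what happens when counts are very low. Neither states an expected MACE rate or a MACE margin. SAP Section 2.4.5 describes the safety analysis as descriptive, without systematic tests.

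**The concern.** The usual large-sample interval for a difference in proportions takes its variance from the observed proportions. With no event in either arm that variance is zero, and only the continuity term is left. The width then depends on the sample size alone and says nothing about how much risk the data still allow. With one or two events the variance is positive but still too small.

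This matters because protocol Section 2.3 singles out cardiac events for adjudication and regular review by the Data Monitoring Committee. In a descriptive analysis the interval is the reader's main guide to how large a cardiovascular excess remains compatible with the data. An interval that is narrowest when there is least information reads as more reassuring than it should.

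**Working it through.** **Inputs.** 462 per arm (SAP Section 1.3), assumed equal to the safety population. Interval: 95%, asymptotic, continuity corrected (SAP Section 2.4.5.1). Reading it as Wald plus (1/n1 + 1/n2)/2 is an assumption. True MACE risks are not in the documents, so a range is assumed.

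**The plan's own figure.** The documents give no figure for this interval; the nearest stated figure on the same sample size is the 90% power for exacerbations. From SAP Section 1.3 (placebo rate 1.5, dupilumab rate 1.125, dispersion 1, 0.95 year, two-sided 0.049):

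- Variance of the log rate ratio = [1/(1.5 × 0.95) + 1/(1.125 × 0.95) + 2]/462 = (0.702 + 0.936 + 2)/462 = 0.00787, so the standard error is 0.0887.
- |ln 0.75| / 0.0887 = 0.2877/0.0887 = 3.24; 3.24 − 1.97 = 1.27; power = 89.9%.

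This reproduces the stated 90%, so 462 per arm is used below.

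**Planned interval.** With p1 = x1/462 and p2 = x2/462:

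d ± {1.96 × √[p1(1 − p1)/462 + p2(1 − p2)/462] + 1/462}, where 1/462 = 0.216%.

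- 0 v 0: the root is 0, so the interval is ±0.216%.
- 1 v 0: d = 0.216% and the Wald part is 0.424%; upper limit 0.216 + 0.424 + 0.216 = 0.86%.

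**Comparison with the Miettinen-Nurminen score interval** (events dupilumab v placebo, upper limit of dupilumab minus placebo):

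| Events | Planned | Score | Planned/score |
|---|---|---|---|
| 0 v 0 | 0.22% | 0.83% | 0.26 |
| 1 v 0 | 0.86% | 1.22% | 0.70 |
| 1 v 1 | 0.82% | 1.02% | 0.80 |
| 2 v 0 | 1.25% | 1.57% | 0.80 |
| 2 v 2 | 1.06% | 1.18% | 0.90 |
| 5 v 5 | 1.55% | 1.56% | 1.00 |
| 10 v 10 | 2.09% | 2.03% | 1.03 |

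Newcombe's interval also gives ±0.83% at 0 v 0. The exact 97.5% upper limit for a single arm with 0/462 is 1 − 0.025^(1/462) = 0.80%, so about 0.8% is a sound benchmark.

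**Exact coverage**, by enumerating two binomials with n = 462:

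| True risks | Planned | Score |
|---|---|---|
| 0.30% v 0.05% | 80% | 99% |
| 0.35% v 0.10% | 87% | 98% |
| 0.5% v 0.1% | 93% | 97% |
| 1% v 1% | 98% | 96% |
| 2% v 2% | 97% | 95% |
| 3% v 3% | 97% | 95% |

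The first row is almost entirely the 0 v 0 outcome. Its probability is 0.997^462 × 0.9995^462 = 0.198, and the interval of ±0.216% then misses the true difference of 0.25%.

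**How likely low counts are**, at an assumed common risk p in both arms:

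| p | Chance of 0 v 0, (1 − p)^924 | Chance of 2 or fewer events in total |
|---|---|---|
| 0.1% | 40% | 93% |
| 0.2% | 16% | 72% |
| 0.5% | 1% | 16% |
| 1% | 0.01% | 0.5% |

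**The case against.** Five points can be made against the concern.

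- **A reader might infer that the interval collapses whenever events are few, say at 0 to 2.** The figures do not support that. Collapse occurs only at 0 v 0; with one or two events the limit is too low by about 10 to 30%.
- **A reader might infer from exclusion criteria E20 to E26 that MACE will be very rare.** The documents do not establish this. E20 to E22 and E26 use six-month windows, so older events remain eligible. Patients are 40 to 80 years old with at least 10 pack-years, and protocol Section 2.3 describes cardiovascular disease as common in COPD. At a risk of 1% or more in both arms, the planned interval is mildly conservative for MACE overall.
- **A reader might infer that each MACE component will get this interval.** SAP Section 2.4.5.1 has one risk-difference line under the MACE heading, and Section 2.1.4.1 lists the composites without prescribing an interval for each. Single components are where 0 v 0 is most plausible, but that analysis is not stated.
- **A reader might infer that the interval will be used to rule out harm.** No margin, hypothesis or decision rule depends on it. The SAP also plans counts by arm, a listing of all events sent for adjudication and Kaplan-Meier plots, so zero events would be plain to see.
- **Score intervals are asymptotic too**, so the Wald reading is the usual one but not a stated fact.

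All five stand as limits on scope and severity. None makes the interval, on its usual reading, correct at very low counts, and event listings do not supply a bound on the difference.

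**Conclusion.** The point holds in a limited form, and its severity is minor. On the usual reading of the wording, the planned interval is miscalibrated in both directions: about 3.8 times too narrow at 0 v 0 (0.83/0.22), modestly too narrow at one or two events, and slightly too wide once events are common. Coverage well below 95% requires very low risks with a real excess, such as 0.30% v 0.05%.

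This rests on three assumptions: that asymptotic means Wald with the standard correction, that about 462 patients per arm are treated, and that the true MACE risk lies in a range the documents do not give. If the risk is 1% or more per arm, the practical effect on overall MACE is slight over-coverage. The consequence is limited to how the reported interval reads.

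**What to change.** In SAP Section 2.4.5.1 and in the MACE row of protocol Table 10, replace the description of the interval with the Miettinen-Nurminen (or Newcombe) score 95% confidence interval for the risk difference. State that the same interval applies to any other adjudicated cardiovascular category for which a risk difference is reported.

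The cost is one phrase in each document. Data collection, sample size and alpha are unaffected. Bounds for very rare events become wider, which reflects what the data can show; at around five events per arm the results barely change.
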